#### 4.5.5.3 Physical and Neurological Examination

A complete physical examination and complete neurological examination was performed at baseline and at Months 12, 24, and 36. Brief neurological examinations were also performed at all other visits during the open-label extension.

For the 15 items of complete physical exam and 42 items of complete neurological exam, the number and percentage of patients with normal or abnormal results will be presented.

A by-patient listing of physical and neurological examination data will also be provided.

#### 4.5.5.4 AUA Symptom Index

An AUA Symptoms Index, a 7-item Likert-scored scale describing urinary bladder function, is completed by the investigator at the baseline phase, and at Months 1, 3 and 12.

Descriptive statistics (n, mean, std, median, minimum, maximum) of the AUA symptom index scores in each treatment group will be presented by two table layouts: 1) AUA raw overall scores at baseline, Months 1, 3 and 12, 2) change from baseline to Month 1, 2 and 12.

Besides the descriptive statistics tables, AUA symptom index scores will be categorized by using 3 levels: 0-7 as mild, 8-19 as moderate, and >19 as severe. A shift table of the number (%) of patients in the categories of mild, moderate, and severe will be provided.

A listing of AUA symptom index data will be provided.

#### 4.5.5.5 Post-void Residual (PVR) Bladder Ultrasound

PVR bladder ultrasound data are collected at baseline, and at Months 1, 3 and 12 to assess the patient's bladder function.

Descriptive statistics for the PVR bladder ultrasound results and change from baseline at each visit will be presented. The number and percentage of patients with abnormal PVR bladder ultrasound at each visit will also be presented.

In addition, PVR bladder ultrasound scores will be categorized by using 3 levels: >50ml, >100ml and >150ml will also be provided.

A by-patient listing of the PVR Bladder Ultrasound data will also be provided.

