#### **10.3.5. Post-Void Residual (PVR) Bladder Ultrasound**

A post-void residual (PVR) bladder ultrasound to assess urinary retention will be performed at Visits 1, 2, 5, 8, 11 and 14 during the first, second, third, and fourth year of the open-label extension study.

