- In addition to the scheduled pregnancy tests, a pregnancy test should be performed during the study whenever a woman's menstrual period is 5 days late.
- The AUA Symptom Index and the PVR bladder ultrasound will only be performed during the first, second, third, and fourth year of the open-label extension study (Visits 1, 2, 5, 8, 11, and 14).
- Dispensation of study medication is not applicable at the final study visit, if a patient has discontinued early or completed the open-label extension study.
- Study visits added per FDA comments that the open label extension trial should include more frequent hematological monitoring. These are now in-line with the hematological monitoring frequencies per the VRX-RET-E22-302, double-blind trial.

CONFIDENTIAL

RM2009/00475/00  
VRX-RET-E22-304

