This study is the open-label extension of the Phase 3 Study VRX-RET-E22-302. VRX-RETE22-302 is a randomized, double-blind, placebo-controlled, parallel-group, multicenter, study of 900 mg/day and 600mg/day retigabine versus placebo. During the 4-week titration phase patients are titrated to the target dose. 510 patients are expected to be randomized to treatment. A 12-week maintenance phase follows. All patients who wish to enter the open-label extension protocol will enter a 4-week transition phase in which their dose will be titrated to 300 mg TID in order to maintain the blind to the maximum extent. Thereafter, the patients could enter this extension study (Study VRX-RET-E22-304). Patients who do not wish to enter the open-label extension protocol will have their dose tapered over a 3-week period.

This Statistical Analysis Plan (SAP) was created according to Protocol VRX-RET-E22-304, Amendment 1 (July 2, 2007).

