4. All patients who discontinue early from study treatment during the open-label extension study will have their study medication tapered over a 3-week period, reducing their daily dose by one third per week, and then return for a final visit. Patients who discontinue early during the first year of the open-label extension study will complete all assessments and evaluations scheduled for Study Visit 5. Patients who discontinue early during the second year of the open-label extension study will complete all assessments and evaluations scheduled for Study Visit 8. Patients who discontinue early during the third year of the open-label extension study will complete all assessments and evaluations scheduled for Study Visit 11. Also, all adverse events should be followed and collected up to until 30 days after administration of the last dose of study drug (end of study drug taper-off).
5. Supine and standing blood pressure, heart rate.
6. In addition to the scheduled pregnancy tests, a pregnancy test should be performed during the study whenever a woman's menstrual period is 5 days late.
7. The AUA Symptom Index and the PVR bladder ultrasound will only be performed during the first year of the open-label extension study (Visits 1, 2, and 5).
8. Dispensation of study medication is not applicable at the final study visit, if a patient has discontinued early or completed the open-label extension study.
9. Study visits added per FDA comments that the open label extension trial should include more frequent hematological monitoring. These are now in-line with the hematological monitoring frequencies per the VRX-RET-E22-302, double-blind trial.

6

CONFIDENTIAL

RM2009/00475/00  
VRX-RET-E22-304

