### 3.2.2 Safety Assessments

Safety assessments will be evaluated, based on reports of AEs and results of vital signs (supine and standing blood pressure, pulse, and temperature), weight, clinical laboratory evaluations (blood chemistries, hematology and urinalysis including microscopy), a 12-lead ECG, and physical and neurological examinations. Post-void residual (PVR) bladder ultrasounds to assess urinary retention and the American Urological Association (AUA) Symptom Index to assess urinary voiding function will also be performed during the first year of the open-label extension study.

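### The SAP follows Amendment 1, so AUA and PVR bladder results collected after Year 1 under Amendment 2 enter no summary table

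*SAP*

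**What the plan says.** The SAP identifies its source in section 1: "This Statistical Analysis Plan (SAP) was created according to Protocol VRX-RET-E22-304, Amendment 1 (July 2, 2007". Its bladder schedule follows from that:

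- Section 3.2.2 says AUA and PVR "will also be performed during the first year of the open-label extension study".
- Table 1, footnote 7, says they "will only be performed during the first year of the open-label extension study (Visits 1, 2, and 5").
- Section 4.5.5.4 says the AUA index "is completed by the investigator at the baseline phase, and at Months 1, 3 and 12".
- Section 4.5.5.5 says "PVR bladder ultrasound data are collected at baseline, and at Months 1, 3 and 12", then continues: "Descriptive statistics for the PVR bladder ultrasound results and change from baseline at each visit will be presented".

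The current protocol, Amendment 2, differs. Section 10.3.5 says the PVR ultrasound "will be performed at Visits 1, 2, 5, 8, 11 and 14 during the first, second, third, and fourth year", and section 10.3.6 gives the AUA index the same visits. The Appendix A footnote places both "during the first, second, third, and fourth year of the open-label extension study (Visits 1, 2, 5, 8, 11, and 14"). The Visit 8, 11 and 14 checklists in sections 10.15.3, 10.15.6 and 10.15.9 list both. Section 10.20 sends patients who withdraw in Year 2, 3 or 4 to the Visit 8, 11 or 14 assessments respectively, so those visits include both measures too.

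SAP section 4.8 records no change in study conduct or planned analysis.

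**The concern.** The primary objective is long-term safety and tolerability. Protocol section 10.3 names PVR and AUA as the assessments of urinary retention and voiding function, and section 11.2 commits to analysing both descriptively. Section 10.3.4 explains why the bladder matters here: toxicity was seen in rats and mice. Amendment 2's summary of revisions gives extension of urinary safety assessment beyond Year 1 as the reason for the added visits.

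Run as written, the SAP summarises none of the scheduled AUA and PVR data that the amendment added. A listing gives no denominator, no change from baseline, no shift between AUA severity classes and no proportion above 50, 100 or 150 mL. Those are the summaries that sections 4.5.5.4 and 4.5.5.5 promise for Year 1.

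**Working it through.** The plan states no figure to reproduce, so the check compares schedules.

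**Scheduled post-baseline AUA/PVR months.** Visits are converted with the Amendment 2 flow chart: Visits 1, 2, 5, 8, 11, 14 = Months 1, 3, 12, 24, 36, 48.

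| Source | 1 | 3 | 12 | 24 | 36 | 48 |
|---|---|---|---|---|---|---|
| Amendment 1 (10.3.5, 10.3.6, flow chart) | X | X | X | | | |
| SAP 4.5.5.4 and 4.5.5.5 | X | X | X | | | |
| SAP Tables 35, 36, 38–41 | X | X | X | | | |
| SAP Table 37 as printed (Month 3 twice) | X | X | | | | |
| Amendment 2 | X | X | X | X | X | X |

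The SAP schedule matches Amendment 1 exactly. Against Amendment 2, Months 24, 36 and 48 are missing.

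**Share without a summary row, by length of follow-up.**

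- To Month 24: {1, 3, 12, 24} less {1, 3, 12} leaves 1 of 4.
- To Month 36: 2 of 5.
- To Month 48: 3 of 6.

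**Whether other SAP wording fills the gap.** The reference to each visit in section 4.5.5.5 follows directly on the sentence that names the visits, and the shells match that sentence. There is no early-termination row, no visit-mapping rule, and no last-value or worst-value bladder table. By contrast, the shells for chemistry, liver tests, urinalysis, ECG, vital signs, examinations and QOLIE-31-P all run to Month 36. Among the visit-based safety measures repeated after Year 1, only AUA and PVR stop at Month 12.

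**When the data could arise.** Protocol section 10.1 defines a month as 30 days. Section 22 requires ethics approval before a change is applied. The approval lag is not given, so 0, 90 and 180 days are assumed. Month 24 AUA/PVR applies to patients who entered on or after

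14 Aug 2008 + lag − 24 × 30 days,

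which gives 25 Aug 2006, 23 Nov 2006 or 21 Feb 2007.

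Counting from the original protocol date (10 Feb 2006) as an early bound, the first nominal dates are:

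- Month 24: + 720 days = 31 Jan 2008, which is 196 days before Amendment 2.
- Month 36: + 1,080 days = 25 Jan 2009.
- Month 48: + 1,440 days = 20 Jan 2010.

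These dates are nominal; the visit window is ±7 days. Some early entrants could have passed Month 24 before the amendment, but every Month 36 and Month 48 visit falls after its date.

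**The case against.** The strongest reply is that this is a version lag and not a faulty analysis. The SAP agrees with the amendment it names. Its date and data cut-off are not visible in the copy reviewed, so section 4.8 may have been true when written. The tables are descriptive, no test depends on them, and every result is still listed. All of that is correct. It explains the mismatch without removing it: the SAP still states a first-year restriction that the current protocol has dropped. Every safety summary in this SAP is descriptive, so a missing row is a missing analysis.

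A second reply is that few data may be affected. The fractions above count scheduled slots, and a patient who passed Month 24 before local approval has no Month 24 result to lose. Month 48 rows may be empty. The German addendum projected a study end at the close of 2008, before any Month 36 visit, so unless that was extended German sites add nothing at Month 36 or 48. This limits what can be said about size. It does not touch Month 24 visits or later-year withdrawals after local approval.

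Third, the sentence in protocol section 10.3.4 asking for careful attention names creatinine, BUN, urine microscopy and symptoms, and not AUA or PVR. Chemistry and urinalysis are tabulated to Month 36, adverse events cover the whole period, and Table 33 includes abdomen and genitalia. So some long-term bladder evidence would be summarised. The two instruments dedicated to voiding and retention would not be.

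Fourth, the SAP has no mapping rule for any withdrawal visit, including those in Year 1. True, but a Year 1 withdrawal at least has a Month 12 row it could go to. Later ones have none.

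**Conclusion.** The concern holds. All seven AUA/PVR tables lack every row after Year 1, although Amendment 2 schedules three further assessments and repeats them at Year 2 to 4 withdrawal visits. Followed exactly, the SAP leaves those results out of every summary. Because they bear on the primary objective, this should be corrected before the analysis is run.

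The number of results affected is unknown; it depends on entry dates, local approval dates and the data cut-off, none of which is given. If the report number on the pages (RM2009) means a 2009 report, which is only an inference, Month 48 rows would be empty and Month 36 sparse, and Month 24 would be the main loss.

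A lesser consequence of the same lag is that the 14 by-visit tables 22 to 34 and 43 stop at Month 36, although Visits 12 to 14 (Months 40, 44 and 48) are scheduled. Whole-period tables for adverse events, deaths, withdrawals and exposure still include Year 4.

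**What to change.** Re-issue the SAP against Amendment 2.

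1. **Main change.** Add Months 24 and 36, and Month 48 if reached, to sections 4.5.5.4 and 4.5.5.5 and to Tables 35 to 41. Show n per row, because patients who passed Month 24 before local approval have no result there. State which row holds AUA and PVR results from withdrawal visits in Years 2 to 4. A separate row is advisable, since protocol section 9.7.5 places those assessments after the taper.
2. **Secondary, where data exist.** Add Months 40, 44 and 48 to Tables 22–26, 31, 32 and 34, and Month 48 to Tables 27–30, 33 and 43. Longer efficacy cohorts are optional.
3. **Consistency.** Update section 1, section 3.2.2, Table 1 with its footnotes, and section 4.8.

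Three separate slips can be corrected in the same re-issue. Section 4.5.5.4 gives AUA change at Months 1, 2 and 12 where Table 36 uses 1, 3 and 12. The second Month 3 block in Table 37 should be Month 12. The exposure classes are in weeks in section 4.5.1 and in months in Table 14.

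The cost is SAP wording and extra rows in existing shells. No new data or procedures are needed.

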#### 4.5.6 Concomitant Medications

Any on-going medications, including prescription and non-prescription as well as vitamins and herbal supplements, and any new medications taken during the study should be recorded on the Concomitant Medication Record form. The concomitant medications will be coded according to the World Health Organization (WHO) Drug Dictionary. The number and percentage of concomitant medications will be summarized in tables.

A by-patient listing of all concomitant medications will also be provided.

#### 4.6 Quality of Life in Epilepsy (QOLIE-31-P)

The patient-weighted 31-item questionnaire (QOLIE-31-P, version 2.0) was administered in this study, describing health-related quality of life in people with epilepsy. The QOLIE-31-P form will be completed by the patient at baseline phase and at Months 3, 6, 9, 12, 24, and 36. Subscale and total scores will be calculated and the subscales grouped into two factors: emotional/psychological effects (seizure worry, overall QOL, emotional well-being, energy/fatigue subscales) and medical/social effects (medication effects, work-driving-social limits, cognitive function subscales).

Descriptive statistics of the QOLIE-31-P data will be presented in the tables and listings for

- Overall assessment
- Emotional/Psychological Effects domain
- Medical/Social Effects domain.

#### 4.7 Determination of Sample Size

All participants who have successfully completed the Maintenance and Transition phases of Study VRX-RET-E22-302, for the treatment of partial-onset seizures are eligible (up to approximately 510 patients).

#### 4.8 Changes in the Conduct of the Study or Planned Analysis

No changes in the conduct of the study or planned analysis have occurred.

### 6 REPORTING OUTPUT

All outputs will be produced using SAS® version 9.1.3 or a later version (if available at PAREXEL). The REPORT procedure will be used to produce all tables and listings whenever possible. The Gplot procedure will be used to produce all figures whenever possible. All statistical appendices (supportive SAS output) will be output directly from the appropriate SAS procedure.

Post-text tables, listings and statistical appendices will be produced as RTF files using ODS and Courier New font size 9. Figures will be produced as RTF files using ODS and font=simplex. For all outputs, the page numbering will be applied to ensure that when the RTF files are combined, the page numbering remains fixed.

## 7 LIST OF TABLES

TABLE 1 NUMBER (%) OF PATIENTS WHO DISCONTINUED TREATMENT DURING THERAPY PHASE BY PRIMARY REASON

TABLE 2 TIME UNTIL TREATMENT DISCONTINUATION (DAYS) DESCRIPTIVE STATISTICS

TABLE 3 DEMOGRAPHIC AND BASELINE CHARACTERISTICS

TABLE 4 EPILEPSY HISTORY

TABLE 5 CLINICAL GLOBAL IMPRESSION (CGI) – SEVERITY AT BASELINE

TABLE 6 NUMBER OF BACKGROUND AEDs AT BASELINE N (%)

TABLE 7 PRESENCE OF PARTIAL SEIZURE BY SUBTYPE DURING BASELINE PERIOD

TABLE 9.1 PERCENTAGE CHANGE IN MONTHLY TOTAL PARTIAL SEIZURE FREQUENCY FOR PATIENTS TREATED WITH RETIGABINE FOR AT LEAST 1 MONTH DURING THE OPEN-LABEL EXTENSION

TABLE 9.2 PERCENTAGE CHANGE IN MONTHLY TOTAL PARTIAL SEIZURE FREQUENCY FOR PATIENTS TREATED WITH RETIGABINE FOR AT LEAST 3 MONTHS DURING THE OPEN-LABEL EXTENSION

TABLE 9.3 PERCENTAGE CHANGE IN MONTHLY TOTAL PARTIAL SEIZURE FREQUENCY FOR PATIENTS TREATED WITH RETIGABINE FOR AT LEAST 6 MONTHS DURING THE OPEN-LABEL EXTENSION

TABLE 9.4 PERCENTAGE CHANGE IN MONTHLY TOTAL PARTIAL SEIZURE FREQUENCY FOR PATIENTS TREATED WITH RETIGABINE FOR AT LEAST 9 MONTHS DURING THE OPEN-LABEL EXTENSION

TABLE 9.5 PERCENTAGE CHANGE IN MONTHLY TOTAL PARTIAL SEIZURE FREQUENCY FOR PATIENTS TREATED WITH RETIGABINE FOR AT LEAST 12 MONTHS DURING THE OPEN-LABEL EXTENSION

TABLE 9.6 PERCENTAGE CHANGE IN MONTHLY TOTAL PARTIAL SEIZURE FREQUENCY FOR PATIENTS TREATED WITH RETIGABINE FOR AT LEAST 16 MONTHS DURING THE OPEN-LABEL EXTENSION

TABLE 9.7 PERCENTAGE CHANGE IN MONTHLY TOTAL PARTIAL SEIZURE FREQUENCY FOR PATIENTS TREATED WITH RETIGABINE FOR AT LEAST 20 MONTHS DURING THE OPEN-LABEL EXTENSION

TABLE 9.8 PERCENTAGE CHANGE IN MONTHLY TOTAL PARTIAL SEIZURE FREQUENCY FOR PATIENTS TREATED WITH RETIGABINE FOR AT LEAST 24 MONTHS DURING THE OPEN-LABEL EXTENSION

TABLE 9.9 PERCENTAGE CHANGE IN MONTHLY TOTAL PARTIAL SEIZURE FREQUENCY FOR PATIENTS TREATED WITH RETIGABINE FOR AT LEAST 28 MONTHS DURING THE OPEN-LABEL EXTENSION

TABLE 9.10 PERCENTAGE CHANGE IN MONTHLY TOTAL PARTIAL SEIZURE FREQUENCY FOR PATIENTS TREATED WITH RETIGABINE FOR AT LEAST 32 MONTHS DURING THE OPEN-LABEL EXTENSION

TABLE 9.11 PERCENTAGE CHANGE IN MONTHLY TOTAL PARTIAL SEIZURE FREQUENCY FOR PATIENTS TREATED WITH RETIGABINE FOR AT LEAST 36 MONTHS DURING THE OPEN-LABEL EXTENSION

- TABLE 10 RESPONDER RATE ( $\geq 50\%$  REDUCTION IN MONTHLY TOTAL PARTIAL SEIZURE FREQUENCY)
- TABLE 11.1 RESPONDER RATE ( $\geq 50\%$  REDUCTION IN MONTHLY TOTAL PARTIAL SEIZURE FREQUENCY) FOR PATIENTS TREATED WITH RETIGABINE FOR AT LEAST 1 MONTH DURING THE OPEN-LABEL EXTENSION
- TABLE 11.2 RESPONDER RATE ( $\geq 50\%$  REDUCTION IN MONTHLY TOTAL PARTIAL SEIZURE FREQUENCY) FOR PATIENTS TREATED WITH RETIGABINE FOR AT LEAST 3 MONTHS DURING THE OPEN-LABEL EXTENSION
- TABLE 11.3 RESPONDER RATE ( $\geq 50\%$  REDUCTION IN MONTHLY TOTAL PARTIAL SEIZURE FREQUENCY) FOR PATIENTS TREATED WITH RETIGABINE FOR AT LEAST 6 MONTHS DURING THE OPEN-LABEL EXTENSION
- TABLE 11.4 RESPONDER RATE ( $\geq 50\%$  REDUCTION IN MONTHLY TOTAL PARTIAL SEIZURE FREQUENCY) FOR PATIENTS TREATED WITH RETIGABINE FOR AT LEAST 9 MONTHS DURING THE OPEN-LABEL EXTENSION
- TABLE 11.5 RESPONDER RATE ( $\geq 50\%$  REDUCTION IN MONTHLY TOTAL PARTIAL SEIZURE FREQUENCY) FOR PATIENTS TREATED WITH RETIGABINE FOR AT LEAST 12 MONTHS DURING THE OPEN-LABEL EXTENSION
- TABLE 11.6 RESPONDER RATE ( $\geq 50\%$  REDUCTION IN MONTHLY TOTAL PARTIAL SEIZURE FREQUENCY) FOR PATIENTS TREATED WITH RETIGABINE FOR AT LEAST 16 MONTHS DURING THE OPEN-LABEL EXTENSION
- TABLE 11.7 RESPONDER RATE ( $\geq 50\%$  REDUCTION IN MONTHLY TOTAL PARTIAL SEIZURE FREQUENCY) FOR PATIENTS TREATED WITH RETIGABINE FOR AT LEAST 20 MONTHS DURING THE OPEN-LABEL EXTENSION
- TABLE 11.8 RESPONDER RATE ( $\geq 50\%$  REDUCTION IN MONTHLY TOTAL PARTIAL SEIZURE FREQUENCY) FOR PATIENTS TREATED WITH RETIGABINE FOR AT LEAST 24 MONTHS DURING THE OPEN-LABEL EXTENSION
- TABLE 11.9 RESPONDER RATE ( $\geq 50\%$  REDUCTION IN MONTHLY TOTAL PARTIAL SEIZURE FREQUENCY) FOR PATIENTS TREATED WITH RETIGABINE FOR AT LEAST 28 MONTHS DURING THE OPEN-LABEL EXTENSION
- TABLE 11.10 RESPONDER RATE ( $\geq 50\%$  REDUCTION IN MONTHLY TOTAL PARTIAL SEIZURE FREQUENCY) FOR PATIENTS TREATED WITH RETIGABINE FOR AT LEAST 32 MONTHS DURING THE OPEN-LABEL EXTENSION
- TABLE 11.11 RESPONDER RATE ( $\geq 50\%$  REDUCTION IN MONTHLY TOTAL PARTIAL SEIZURE FREQUENCY) FOR PATIENTS TREATED WITH RETIGABINE FOR AT LEAST 36 MONTHS DURING THE OPEN-LABEL EXTENSION

TABLE 12 PROPORTION OF PATIENTS EXPERIENCING A REDUCTION IN MONTHLY TOTAL PARTIAL SEIZURE FREQUENCY

TABLE 13 PROPORTION OF SEIZURE-FREE DAYS

TABLE 14 EXTENT OF EXPOSURE TO STUDY MEDICATION

TABLE 15 NUMBER (%) OF PATIENTS REPORTING TREATMENT-EMERGENT ADVERSE EVENTS

TABLE 16 NUMBER (%) OF PATIENTS REPORTING ADVERSE EVENTS BY MAXIMUM SEVERITY

TABLE 17 NUMBER (%) OF PATIENTS REPORTING TREATMENT-EMERGENT ADVERSE EVENTS AT LEAST POSSIBLY RELATED TO STUDY DRUG

TABLE 18 NUMBER (%) OF PATIENTS REPORTING TREATMENT-EMERGENT ADVERSE EVENTS THAT LEAD TO DOSE MODIFICATION/INTERRUPTION

TABLE 19 NUMBER (%) OF PATIENTS REPORTING FATAL TREATMENT-EMERGENT ADVERSE EVENTS

TABLE 20 NUMBER (%) OF PATIENTS REPORTING SERIOUS TREATMENT-EMERGENT ADVERSE EVENTS

TABLE 21 NUMBER (%) OF PATIENTS REPORTING ADVERSE EVENTS THAT CAUSED WITHDRAWAL FROM STUDY

TABLE 22 OBSERVED MEANS AND STANDARD DEVIATIONS OF LABORATORY TEST RESULTS AND CHANGE FROM BASELINE BY MONTH - SERUM CHEMISTRY

TABLE 24 OBSERVED MEANS AND STANDARD DEVIATIONS OF LABORATORY TEST RESULTS AND CHANGE FROM BASELINE BY MONTH – HEMATOLOGY

TABLE 25 OBSERVED MEANS AND STANDARD DEVIATIONS OF LABORATORY TEST RESULTS AND CHANGE FROM BASELINE BY MONTH – URINALYSIS

TABLE 23 NUMBER (%) OF PATIENTS WITH CLINICALLY SIGNIFICANT LIVER FUNCTION TEST RESULTS

TABLE 26 FREQUENCY DISTRIBUTION OF CATEGORICAL LABORATORY TEST RESULTS - URINALYSIS

TABLE 27 SUMMARY STATISTICS OF ELECTROCARDIOGRAM MEASURES

TABLE 28 NUMBER (%) OF PATIENTS EXAMINING QTC INTERVAL BY CATEGORY

TABLE 29 NUMBER (%) OF PATIENTS EXAMINING QTC INTERVAL CHANGE FROM BASELINE BY CATEGORY

TABLE 30 OBSERVED MEANS AND STANDARD DEVIATIONS OF QTC INTERVALS AND CHANGE FROM BASELINE BY MONTH

TABLE 31 OBSERVED MEANS AND STANDARD DEVIATIONS OF VITAL SIGN RESULTS AND CHANGE FROM BASELINE BY MONTH

TABLE 33 NUMBER (%) OF PATIENTS WITH ABNORMAL RESULTS OF PHYSICAL EXAMINATIONS

TABLE 34 NUMBER (%) OF PATIENTS WITH ABNORMAL RESULTS OF NEUROLOGICAL EXAMINATIONS

TABLE 35 NUMBER (%) OF PATIENTS WITH ABNORMAL AUA SYMPTOM INDEX

TABLE 36 DESCRIPTIVE STATISTICS OF RAW OVERALL AUA SCORES  
TABLE 37 NUMBER (%) OF PATIENTS WHO HAD MILD, MODERATE, SEVERE  
AUA SCORES  
TABLE 38 AUA CATEGORY SHIFT FROM BASELINE  
TABLE 39 NUMBER (%) OF PATIENTS WITH ABNORMAL PVR BLADDER  
ULTRASOUND  
TABLE 40 DESCRIPTIVE STATISTICS OF PVR BLADDER ULTRASOUND  
TABLE 41 NUMBER (%) OF PATIENTS WITH A CLINICALLY SIGNIFICANT  
PVR BLADDER ULTRASOUND  
TABLE 42 NUMBER (%) OF PATIENTS TAKING CONCOMITANT  
MEDICATIONS  
TABLE 43 OBSERVED MEANS AND STANDARD DEVIATIONS OF QOL IN  
EPILEPSY (QOLIE-31-P) AND CHANGE FROM BASELINE BY MONTH

